9.1.2 Dose Modification

TMZ will be administered concomitantly with standard external beam RT under the direction of the oncologist. Please see TMZ package insert uploaded in electronic IRB for standard of care treatment guidelines. The dose of the concomitant TMZ with RT may be adjusted at the discretion of the treating oncologist.

The study drug (CMV pp65 RNA-pulsed DCs with GM-CSF) dose will not be modified in this trial. Those subjects whose cells fail to meet release criteria will be removed and replaced.

9.1.3 Safety Considerations

Management of Toxicities

If a Grade 3 NCI CTC or greater toxicity is seen that is not attributable to a concomitant medication, co-morbid event, or disease progression that has been documented radiographically or clinically, the next immunization for that patient will be withheld for up to 2 months or until the NCI CTC toxicity improves to a Grade 1 or less. However, planned procedures requiring hospitalization, or long-term clinical decline that is now seen in patients years from whole brain radiation therapy (WBRT), which are clearly not related to study drug, but are the natural development common in this patient population, will not be considered an unacceptable toxicity nor will have immunizations withheld.

Special Consideration

Due to the impact of high dose steroids on the development of an optimal immune response, if a patient demonstrates neurologic or cerebral radiographic signs suggestive of a localized inflammatory reaction, secondary to the immune response triggered by DC vaccination, that requires an increase in dexamethasone dose, every effort should be made to not increase the dose above 4 mg per day at any time. Instead, patients should be treated with bevacizumab at the reduced dose of 7.5 mg/kg IV approximately every 3 weeks. If a patient requires planned treatment for their tumor with bevacizumab > 7.5 mg/kg approximately every 3 weeks, they will be considered off study and enter the follow-up phase. Neuroimaging (MRI) will be performed according to protocol schedule and, at that time, it will be assessed whether further treatment with bevacizumab is needed to control the cerebral inflammation. Bevacizumab will not be provided by the study. Every attempt should be made to reduce or discontinue dexamethasone, when clinically possible, so as not to mitigate immune response.

If there are AEs or other circumstances prohibiting the use of bevacizumab, corticosteroids, surgery, or other interventions deemed more appropriate for the patient by the treating physician will be used, if needed, to treat any localized inflammatory reaction secondary to DC vaccination.

Adverse Event Reporting and Documentation

An “Adverse Event” will be defined as any adverse change from the subject’s pre-treatment baseline condition (which is assessed at the post-RT/TMZ clinic visit), including any clinical or laboratory test abnormality that occurs during the course of research. Adverse events will be categorized and graded in accordance with the NCI CTCAE (Version 5).

A “Serious Adverse Event” will be defined as an undesirable sign, symptom or medical condition which: 1) is fatal or life threatening; 2) requires inpatient hospitalization for > 24 hours or a prolongation of existing hospitalization; 3) results in persistent or significant disability/incapacity; 4) constitutes a congenital anomaly or a birth defect and/or; 5) medically significant such that it may jeopardize the subject, and may require medical or surgical intervention to prevent one of the outcomes listed above.

A summary of all adverse events (not just those considered related to study drug) that occur following RT/TMZ will be kept which will categorize the event by organ system, relationship to treatment, its grade of severity, and resolution. Periodic review by the primary investigator (PI) and weekly review at the Duke Preston Robert Tisch Brain Tumor Center (PRTBTC) Adverse Event (AE) meeting of the collective adverse events will occur with the intention of identifying any trends or patterns in toxicity. If any such trends are identified, depending on their severity and frequency, a protocol amendment will be considered.

All adverse events which are serious and unexpected should be reported immediately to [name] M.D. at [contact] during regular business hours or at [name] after hours and to the Federal Drug Administration (FDA). Fatal or life-threatening, unexpected adverse events will be reported to the FDA by telephone, facsimile, or in writing as soon as possible, but no later than 7 calendar days after first knowledge by the sponsor followed by as complete a report as possible within 8 additional calendar days. Serious, unexpected adverse events that are not fatal or life-threatening will be reported to the FDA by telephone, facsimile, or in writing as soon as possible, but no later than 15 calendar days after first knowledge by the sponsor.

All adverse events that are considered serious, unanticipated, and related or possibly related to the research (as defined by 21CRF312.32[a]) will be reported to the Duke University Medical Center Institutional Review Board (IRB) using the appropriate serious adverse event (SAE) report form. At the time of the annual progress report to the Duke University Medical Center IRB, a summary of the overall toxicity experience will be provided.

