13 SAFETY MONITORING AND REPORTING

13.1 Adverse Events

An AE is any untoward medical occurrence in a subject receiving pre-conditioning or the study vaccine and which does not necessarily have a causal relationship with this treatment. For this protocol, the definition of AE also includes worsening of any pre-existing medical condition. An AE can therefore be any unfavorable and unintended or worsening sign (including an abnormal laboratory finding), symptom, or disease temporally associated with the use of the DCs, whether or not related to use of the DCs. Abnormal laboratory findings without clinical significance (based on the PI's judgment) should not be recorded as AEs. But, laboratory value changes that require therapy or adjustment in prior therapy are considered adverse events.

Adverse events will be collected from the time of administration of the first DC vaccine through 1 month after the subject's last vaccine, all AEs must be recorded in the subject's medical record and adverse events case report form.

AEs will be assessed according to the CTCAE version 5. If CTCAE grading does not exist for an AE, the severity of the AE will be graded as mild (1), moderate (2), severe (3), life-threatening (4), or fatal (5).

Attribution of AEs will be indicated as follows:

- Definite: The AE is clearly related to the study drug
- Probably: The AE is likely related to the study drug
- Possible: The AE may be related to the study drug
- Unlikely: The AE is doubtfully related to the study drug
- Unrelated: The AE is clearly NOT related to the study drug

Attribution of AEs will be determined for each study intervention individually (pp65 DC vaccine, pre-conditioning agent [Td], TMZ, bevacizumab).

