13.1.1 Reporting of AEs

A summary of all adverse events (not just those considered related to the study drug) will be kept which will categorize the event by organ system, relationship to which treatment, its grade of severity, and resolution. Periodic review by the PI and monthly review at the PRTBTC Adverse Event meeting of the collective adverse events will occur with the intention of identifying any trends or patterns in toxicity. If any such trends are identified, depending on their severity and frequency, a protocol amendment will be considered.

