13.3 Serious Adverse Events

An AE is considered “serious” if in the opinion of the investigator it is one of the following outcomes:

- Fatal
- Life-threatening
- Constitutes a congenital anomaly or birth defect
- A medically significant condition (defined as an event that compromises subject safety or may require
- medical or surgical intervention to prevent one of the three outcomes above).
- Requires inpatient hospitalization or prolongation of existing hospitalization
- Results in persistent or significant incapacity or substantial disruption to conduct normal life functions.

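### Sections 9.1.3 and 13 give conflicting rules for what counts as an SAE, which AEs are recorded and from when, how often they are reviewed, and what is reported immediately

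*Combined protocol and SAP*

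**What the plan says.** All of the text below is in the body of the protocol, not in the amendment log.

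- **Hospitalization as an SAE criterion.** Section 9.1.3: "requires inpatient hospitalization for > 24 hours or a prolongation of existing hospitalization". Section 13.3: "Requires inpatient hospitalization or prolongation of existing hospitalization".
- **Medical significance as an SAE criterion.** Section 9.1.3 includes an event that "may require medical or surgical intervention to prevent one of the outcomes listed above". Section 13.3 refers to "medical or surgical intervention to prevent one of the three outcomes above"; the three items before it are death, threat to life, and congenital anomaly or birth defect.
- **Laboratory findings as AEs.** Section 9.1.3 defines an AE as an adverse change from the post-RT/TMZ baseline, "including any clinical or laboratory test abnormality that occurs during the course of research". Section 13.1 says that "Abnormal laboratory findings without clinical significance", in the PI's judgment, are not to be recorded, but keeps laboratory changes that call for therapy or a change of therapy.
- **Collection window.** Section 9.1.3 keeps a summary of all AEs after RT/TMZ. Section 13.1 collects from the first DC vaccine to one month after the last. Section 13.2 leaves anything earlier unrecorded and unmonitored, apart from leukapheresis events of special interest.
- **Collective review.** Section 9.1.3: "Periodic review by the primary investigator (PI) and weekly review at the Duke Preston Robert Tisch Brain Tumor Center". Section 13.1.1: "Periodic review by the PI and monthly review at the PRTBTC Adverse Event meeting".
- **Immediate reporting.** Section 9.1.3 applies it to events that are both serious and unexpected; Section 13.3.1 applies it to every SAE.

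**The concern.** Two parts of one protocol cover the same ground with near-parallel text, and the details differ. Staff who follow Section 9.1.3 and staff who follow Section 13 would classify some events differently and would start recording at different times. The SAE count would then depend on which page was used.

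The collection window matters most for the analysis. Secondary objective 5 (Section 15.6.5) is the safety of DI-TMZ followed by vaccination, in all patients who initiate DI-TMZ, and Section 15.2 uses the same set for the toxicity summaries. If recording starts at vaccine 1, those summaries lack the DI-TMZ period for a set that is defined by starting DI-TMZ. Section 13.1 also asks for attribution to TMZ as a separate intervention, which sits badly with not recording events while TMZ is being given.

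The hospitalization rule matters because short stays after an injection reaction are foreseeable in a vaccine trial: the legend to Figure 4 mentions an anaphylactic episode in an earlier subject.

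**Working it through.** The plan gives no figure to reproduce here. The check sets the rules side by side, with a little calendar arithmetic.

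**1. Seriousness.** Take two events that meet no other criterion.
- Event A is an inpatient stay of 24 hours or less. It is an SAE under 13.3 and not under 9.1.3.
- Event B may need intervention to avert hospitalization or disability, but not death, threat to life or a birth defect. It can be an SAE under 9.1.3. Under the intervention part of 13.3 it is not. Section 13.3 also has an alternative for events that compromise the subject's safety, so B is lost only if the investigator judges that this does not apply.

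So neither definition contains the other: 13.3 is wider on hospitalization, and 9.1.3 is wider on the outcomes to be prevented.

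**2. Laboratory findings.** A worsening from baseline after vaccine 1 that the PI considers not clinically significant is an AE under 9.1.3 and is not recorded under 13.1.

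**3. Collection window.** Vaccine 1 is on day 23 (± 2) of the DI-TMZ cycle (Section 9.1), that is, day 21 to day 25. Counting from day 1:
- shortest: 21 − 1 = 20 days
- nominal: 23 − 1 = 22 days
- longest: 25 − 1 = 24 days

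Any interval between the end of RT/TMZ and day 1 comes on top. A Grade 3 laboratory toxicity in this period is kept under 9.1.3 and not recorded under 13.2. A patient who starts DI-TMZ and never reaches vaccine 1 would be in the toxicity set with no AE data except leukapheresis events. The plan does not say how many such patients to expect. It aims for 48 to start DI-TMZ (Section 15.9) and anticipates 40 at vaccine 4 (Section 15.6.2), so on its own figures at most 48 − 40 = 8. The AE row of Table 4 appears to be marked from main consent onward, which would be a third window; the table is hard to read in the text available, so I put no weight on it.

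**4. Review interval.** Vaccines 1 to 3 are two weeks apart (± 2 days each), so vaccine 1 to vaccine 3 takes 14 + 14 = 28 days, with a minimum of 12 + 12 = 24. Weekly review gives 28 / 7 = 4 meetings in the nominal span. For monthly review, assume a 30-day interval with timing unrelated to the patient's schedule. The chance that at least one meeting falls in the span is 28 / 30 ≈ 93%, or 24 / 30 = 80% at the minimum.

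**5. Immediate reporting.** Serious and unexpected events are a subset of all SAEs. An expected SAE is reported immediately under 13.3.1 only. The FDA limits (7 days plus 8 for the follow-up report, and 15 days) are the same in both sections.

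**6. Link to the suspension rule.** Table A in Section 15.6.5 counts unacceptable toxicities as defined in Section 9.1.1. That definition has no length-of-stay condition, and much of it is tied to Td or the DC vaccine.

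**The case against.** The strongest reply is that little is lost in practice. A short stay is an AE under both sections, and only its label changes; the medical-significance criterion may capture it in any case. Expedited FDA limits agree. Following 13.3.1 satisfies both reporting rules. Section 13.1 can be read as refining the broad AE definition in 9.1.3. Other safeguards exist: AEs are recorded at visits, the PI reviews them periodically, the next immunization is withheld after qualifying toxicity, and Table A and the death rules can suspend accrual. A separate data and safety monitoring plan (Section 16.5) and the DSMBplus charter (Section 13.4) are not in the documents and may settle some of this.

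Most of that stands as a limit on the size of the point. It does not remove the conflict. The 24-hour condition and its absence cannot both apply. One meeting cannot be both weekly and monthly. The refinement reading helps only with laboratory findings, because 13.2 directly contradicts the window in 9.1.3.

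A reader might infer three stronger things, and the documents support none of them:
- That short stays go unreported altogether. They remain AEs.
- That patients would usually receive three vaccines before any collective review. Under the 30-day assumption that happens in about 7% of cases at the nominal spacing and 20% at the minimum. Review frequency in any case affects when a trend is seen, not whether an event is recorded.
- That Section 13 is the more inclusive text and can simply replace 9.1.3. It is narrower on the outcomes to be prevented, on laboratory findings and on the collection window.

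**Conclusion.** The conflicts are real and should be resolved. This is duplicated text that disagrees, not a design choice, and the documents do not show which version was intended.

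The consequences are bounded: whether a stay of 24 hours or less, or an intervention to avert hospitalization or disability, is classed as an SAE; whether AEs in the 20 to 24 days of DI-TMZ before vaccine 1 are recorded; and how soon a pattern is noticed. The second is the most important, since it is where events can go unrecorded and where the AE tables would not match their stated analysis set. The effect on the unacceptable-toxicity proportion and on Table A is likely to be small, for the reasons in step 6 of the working.

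The conclusion assumes that no document outside the protocol sets an order of precedence. The number of events affected cannot be estimated from what is given.

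**What to change.** Reconcile Sections 9.1.3 and 13 into one set of rules in one place, and replace the other text with a cross-reference. Do not carry over Section 13 as it stands.

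- **SAE definition.** Remove the 24-hour qualifier. For medical significance use the 9.1.3 reference to all listed outcomes, and keep the 13.3 alternative for events that compromise the subject's safety, so that no event is lost.
- **AE definition.** State one rule for laboratory findings.
- **Collection window.** State one window that matches the toxicity analysis set, so that it includes the DI-TMZ cycle for every patient who initiates it. Amend 13.1 and 13.2 to agree, and check the AE row of Table 4.
- **Immediate reporting.** Apply it to all SAEs, which satisfies both sections.
- **Review.** State one interval for the AE meeting.

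Check the result against the separate monitoring plan and the DSMBplus charter. The cost is one wording amendment and somewhat more AE and SAE recording, mainly from the DI-TMZ period and short admissions. Sample size and the efficacy analyses are unaffected.

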9.1.4 Missed Doses

To ensure that repetitive DC vaccines will be given to patients, the initial 3 will be given every 2 weeks (\pm 2 days), and the monthly DCs will be given every 35 days (\pm 7 days). Therefore, with a margin of 2 days all patients will receive up to 10 DC vaccines or until progression, whichever comes first. At the discretion of the study PI, patients who miss vaccine administration for whatever reason will have their appointment re-scheduled to administer the vaccine as soon as possible and the study PI will assess whether this deviation needs to be filed with the IRB. For continued non-compliance with the scheduled vaccine appointments, the subject may be removed from the trial at the discretion of the study PI.

9.1.5 Concomitant Medications

Concomitant medications will be managed by the treating oncologist and recorded at each study visit by the study coordinator.

9.2 Rationale for Selection of Dose, Regimen, and Treatment Duration

In our previous randomized clinical trial of 12 patients with newly-diagnosed GBM, we evaluated the impact of vaccine site pre-conditioning with Td toxoid [118]. Patients randomized to Td showed increased dendritic cell migration bilaterally and significantly improved progression-free and overall survival. Furthermore, we observed a modest association between effective DC migration to VDLNs and clinical outcomes. Based on the small sample size of the initial study, we would like to conduct a validation study with Td pre-conditioning that is powered sufficiently to evaluate the impact of DC migration on clinical outcomes.

9.3 Rationale for Correlative Studies

Please see Section 12.7.4 ¹¹¹Indium-labeling of Cells for *in vivo* Trafficking Studies. PLEASE NOTE: With approval of Protocol v.20220204, this correlative study will no longer be conducted.

9.4 Definition of Evaluable Subjects, On Study, and End of Study

Subjects evaluable for the analysis of the primary endpoint of overall survival will include all patients who initiate DI-TMZ.

Once the patient signs an informed consent form (ICF), that subject will be considered “on study.” Rationale for taking patient off protocol treatment will be documented.

9.5 Early Study Termination

This study can be terminated at any time for any reason by the PI-sponsor. If this occurs, all subjects on study should be notified as soon as possible. Additional procedures and/or follow up should occur in accordance with Section 12.6, which describes procedures and process for prematurely withdrawn patients.

10 STUDY DRUG

10.1 Names, Classification, and Mechanism of Action

Tetanus-Diphtheria Toxoid (Td Toxoid adsorbed)

Td is indicated for active booster immunization against tetanus, diphtheria, and pertussis as a single dose; substitute 1-time dose of Tdap for Td booster, then standardly boost with Td every 10 years. Please refer to Section 9.1 on the use of Td in this protocol.

DC Vaccine

Human CMV pp65-LAMP mRNA-pulsed autologous DCs with GM-CSF is the name of the study drug given with every vaccine. This vaccination will then consist of administration of 2×10^7 CMV pp65-LAMP mRNA loaded mature DCs as described above. In up to 16 patients, the fourth vaccine will be labeled with ¹¹¹In (50 μ Ci / 5×10^7 DCs) (Nycomed-Amersham, Chicago, IL) prior to injection. The class of action for all study drugs is a biological with the exception of the tetanus toxoid, which is an antitoxin.

GM-CSF (LEUKINE®; Sargramostim)

GM-CSF will be obtained from commercial supply and stored in the ICS, as a sterile, white, preservative-free powder lyophilized powder in a vial containing 250 mcg to be reconstituted in 0.5 mL of sterile water for injection.

Leukapheresis and Dendritic Cell Vaccine Generation

At least two leukaphereses may be performed on each patient enrolled on this protocol. The leukapheresis will be used for DC generation and immunologic monitoring. If the subjects were part of the companion study (Pro00102797) and have already undergone the leukapheresis procedure the DCs from that study will be used for the current study and any unused vaccine products will be handled as indicated by the patient in the companion study. All leukaphereses will be approximately a 4-hour leukapheresis. It is estimated that 10-12 L of blood will be processed during this leukapheresis. An additional 4-hour leukapheresis will be requested from patients with positive immunological responses to the therapy for additional immunologic monitoring studies or for patients who need additional DCs generated to ensure a total of 10 vaccines.

DCs will be generated from the first leukapheresis *in vitro* by 7-day culture with GM-CSF and IL-4. Peripheral blood mononuclear cells (PBMC) for *in vitro* generation of DCs will be obtained by leukapheresis at the Duke Apheresis Unit and transported to the Cell Processing facility. For patients without sufficient venous access for leukapheresis a temporary intravenous catheter may be inserted.

At the end of the 7 day incubation for generation of DC, a sample of the media is taken for mycoplasma testing, the cells are then harvested and electroporated with pp65-LAMP mRNA. The DCs are placed in a flask with AIM V media GM-CSF + IL-4 + TNF- α + IL-6 + IL-1 β at 37°C, 5% CO₂ for 18-20 hours for maturation. The cells are washed twice with PBS and frozen at 2-4 x 10⁷ cells/mL in 90% autologous human AB serum (Valley Biomedical, Winchester, VA 22602), 10% DMSO and 5% dextrose.

The DCs are then stored until needed at -135°C. After freezing, an aliquot of cells is thawed for QA/QC. This testing will look at viability, (>70%) endotoxin content, (<5 E.U. /Kg B.W.) mycoplasma contamination (negative) and sterility testing for aerobic and anaerobic bacterial cultures (1 x 10⁶ DCs) and fungal cultures (1 x 10⁶ DCs).

For each vaccination, cells that have passed quality assurance/quality control (QA/QC) will be rapidly thawed at 37°C, washed three times with phosphate buffered saline (PBS) and counted. The cell concentration will be adjusted to 5 x 10⁷ cells/mL and DCs will be resuspended in preservative free saline and GM-CSF and placed into a sterile tuberculin syringe with a 25-gauge needle.

For all DC preparations, and ¹¹¹In-labeled DCs, from the final preparation a sample of cells will be sent for Gram stain and endotoxin testing prior to administration. DC vaccination will not be given until endotoxin testing has been passed (< 5.0 E.U./Kg) and the Gram stain has been found

to be negative. An aliquot of cells will also be sent for aerobic and anaerobic bacterial cultures (1×10^6 DCs) and fungal cultures (1×10^6 DCs).

The SOP *MPACT-QA-0017 Responding to Sterility Test Results* describes the roles, responsibilities, and actions that should be taken in the event of a positive, delayed, incomplete, or invalid sterility test result for a product manufactured in the MPACT facility after it has been administered to a study subject. Briefly, personnel informed of the result will notify MPACT Management who is responsible for notifying all relevant study personnel. The Principal Investigator or treating Neuro-Oncologist (or his or her designee) will notify the patient. The patient will be asked to be evaluated by a physician within 48 business hours. Based on the route of administration of the investigational product, appropriate cultures (aerobic, anaerobic, and fungal) will be ordered for the subject (blood cultures or wound cultures) along with CBC and CMP tests. If the patient has or develops a temperature $\geq 38.5^{\circ}\text{C}$ or clinical evidence of infection, the patient will be treated expectantly with antibiotics based on the sensitivities of the organisms identified from the immunization product, as medically necessary. An independent infectious disease consultation will be obtained to guide further therapy if medically necessary. MPACT management and MPACT QA will perform an investigation into the sterility test result. If there are remaining vials from the affected batch, a vial will be sent for repeat sterility testing, and the remainder of the batch will be quarantined until re-testing is complete with negative results. Administration of subsequent products from the affected batch will be held, and upcoming study visits should be rescheduled as necessary. Immunizations will proceed only if the patient fully recovers and subsequent samples are found to be sterile.

